9.1 Permitted Medication(s)

Subjects should receive full supportive care during the study, including transfusion of blood and blood products, and treatment with antibiotics, antiemetics, antidiarrheals, and analgesics, as appropriate. Use of anticoagulants such as warfarin is permitted, however, caution should be exercised and additional International Normalized Ratio (INR) monitoring is recommended when dabrafenib is used concomitantly with warfarin.

9.2 Prohibited Medications

9.2.1 Prohibited Medications: Parts A & B (Trametinib)

There are no prohibited medications while on treatment in Part A and Part B of this study.

9.2.2 Prohibited Medications: Parts C & D (Dabrafenib)

The following medications or non-drug therapies are prohibited while on treatment in Parts C & D of this study:

- Other anti-cancer therapies;
- Other investigational drugs;
- Antiretroviral drugs (Note: Subjects with known human immunodeficiency virus (HIV) are ineligible for study participation);
- Herbal remedies (e.g., St. John’s wort);
- Dabrafenib is metabolized primarily by Cytochrome P450 (CYP) 2C8 and CYP3A4. Co-administration of dabrafenib with ketoconazole, a CYP3A4 inhibition, or with gemfibrozil, a CYP2C8 inhibitor, resulted in increases in dabrafenib AUC of 71% and 47%, respectively. Drugs that are strong inhibitors or inducers of CYP3A and CYP2C8 (see list in [Table 9-1](#)) may only be used under special circumstances (e.g., as a single use for a procedure) while treatment with study drug is interrupted as they may alter dabrafenib concentrations; consider therapeutic substitutions for these medications. Approval by the Medical Lead is required in these situations. The list may be modified based on emerging data. Refer to the SPM for the most current list.

Table 9-1 Prohibited Medications; Parts C and D (Dabrafenib)

PROHIBITED – strong inducers of CYP3A or CYP2C8, since concentrations of dabrafenib may be decreased	
Class/Therapeutic Area	Drugs/Agents
Antibiotics	Rifamycin class agents (e.g., rifampin, rifabutin, rifapentine),
Anticonvulsant	Carbamazepine, phenobarbital, phenytoin, s-mephenytoin
Miscellaneous	bosentan,
PROHIBITED – Strong inhibitors of CYP3A, or CYP2C8 since concentrations of dabrafenib may be increased	
Class/Therapeutic Area	Drugs/Agents
Antibiotics	Clarithromycin, telithromycin, troleandomycin
Antidepressant	Nefazodone
Antifungals	Itraconazole, ketoconazole, posaconazole, voriconazole
Hyperlipidemia	Gemfibrozil
Anti-retroviral	Ritonavir, Saquinavir, Atazanavir
Miscellaneous	Conivaptan

9.3 Medications to be Used with Caution; Parts C & D (Dabrafenib)

The following medications should be used with caution in Parts C and D of this study as their concentrations may be altered by dabrafenib or they may alter dabrafenib concentrations:

- Drugs that are moderate inhibitors or inducers of CYP3A and CYP2C8 as they may alter concentrations of dabrafenib.
- Dabrafenib has been shown to induce CYP3A4 and CYP2C9 in vivo using midazolam (CYP3A4 substrate) and S-warfarin (CYP2C9 substrate). **Dabrafenib** is an in vitro inducer of CYP2B6 and other enzymes such as CYP2C8, CYP2C19, UDP-glucuronyl transferases. Transporters may also be affected. Co-administration of dabrafenib and medications which are affected by the induction of these enzymes (including warfarin) and transporters may result in loss of efficacy. If co-administration of these medications is necessary, investigators should monitor subjects for loss of efficacy or consider substitutions of these medications. A partial list of these medications is provided in [Table 9-2](#) and in the SPM.
- Therapeutic level dosing of warfarin can be used with approval by the Medical Lead and close monitoring of Prothrombin Time/International Normalized Ratio (PT/INR) by the site. Warfarin exposure has been shown to decrease (37% decrease) due to dabrafenib-mediated enzyme induction. Conversely, if dabrafenib dosing is reduced, interrupted, or discontinued, warfarin exposure may be increased. Thus, warfarin dosing may need to be adjusted based on PT/INR during and after treatment with dabrafenib. Prophylactic low dose warfarin may be given to maintain central catheter patency.
- Dabrafenib solubility is pH-dependent with decreased solubility at higher pH. Drugs such as proton pump inhibitors that inhibit gastric acid secretion to elevate gastric pH may decrease the solubility of dabrafenib and reduce its bioavailability. No clinical study has been conducted to evaluate the effect of pH on dabrafenib PK. In an ad-hoc analysis, no differences in C_{max} and AUC were noted between subjects who reported taking pH-elevating products relative to other subjects. Due to the theoretical risk that pH-elevating agents may decrease oral bioavailability and exposure to dabrafenib, these medicinal products that increase gastric pH should be used with caution when administered with dabrafenib.

Table 9-2 Medications to be used with Caution; Parts C and D (Dabrafenib)

USE WITH CAUTION: Moderate inhibitors of CYP3A, or CYP2C8 since concentrations of dabrafenib may be increased	
Class/Therapeutic Area	Moderate CYP3A and CYP2C8 Inhibitors
Antiarrhythmics	Diltiazem, verapamil
Antibiotic	Erythromycin
Antifungal	Fluconazole
Miscellaneous	Aprepitant
USE WITH CAUTION: Co-administration of these drugs with study treatment may result in loss of efficacy. Monitor subjects for loss of efficacy or substitute with another medication.	
Class/Therapeutic Area	CYP3A4, CYP2B6, CYP2C8, CYP2C9, CYP2C19 or Transporter Substrates that May be Affected by Induction
Analgesics	Alfentanil, buprenorphine, celecoxib, codeine, fentanyl, methadone, oxycodone
Antiarrhythmics	Disopyramide, dronedarone, mexiletine, propafenone, quinidine
Antibiotics	Chloramphenicol, doxycycline, erythromycin, moxifloxacin
Anticoagulants/ Antiplatelets	Cilostazole, warfarin

Anticonvulsants	Divalproex, lamotrigine, valproate, zonisamide
Antidepressants and Antipsychotics	Aripiprazole, bupropion, buspirone, desipramine, haloperidol, mirtazapine, pimozide, quetiapine, trazodone, amitriptyline, clomipramine, imipramine
Antidiabetics	Glyburide, saxagliptin, tolbutamide, nateglinide, pioglitazone, repaglinide, rosiglitazone
Antifungals	Caspofungin, fluconazole, terbinafine
Antihistamines	Astemizole, chlorpheniramine, ebastine
Antihypertensives	Amlodipine, diltiazem, felodipine, nifedipine, nilvadipine, nisoldipine, verapamil
Antimigraine Agents	Diergotamine, eletriptan, ergotamine
Corticosteroids	Dexamethasone, methylprednisolone, oral budesonide
Erectile Dysfunction Agents	Sildenafil, tadalafil, vardenafil
HMG-CoA Reductase Inhibitors	Atorvastatin, lovastatin, simvastatin, rosuvastatin, pravastatin
Hypnotics and Sedatives	Alprazolam, brotizolam, diazepam, estazolam, midazolam, triazolam, zolpidem, zopiclone
Immunosuppressants	Everolimus, sirolimus, tacrolimus
Miscellaneous	Aprepitant, cisapride, darifenacin, digoxin, disopyramide, leflunomide, methohexital, oral contraceptives, quinine, ranitidine, solifenacin, sulfasalazine, tramadol, tolvaptan, chloroquine, zopiclone
Selective Aldosterone Blockers	Eplerenone
USE WITH CAUTION: Co-administration of drugs that increase gastric pH should be used with caution when administered with dabrafenib as exposure to dabrafenib may be decreased	
pH altering agents	dexlansoprazole, esomeprazole, famotidine, ilaprazole, lansoprazole, omeprazole, pantoprazole, rabeprazole, ranitidine

Abbreviations: CYP = cytochrome P450; HMG-CoA = 3-hydroxy-3-methylglutaryl-coenzyme A.

Questions regarding concomitant medications should be directed to the Medical Lead for clarification.

10 Lifestyle and/or Dietary Restrictions

10.1 Contraception

10.1.1 Female Subjects

Women of childbearing potential, defined as all women physiologically capable of becoming pregnant, must use highly effective methods of contraception during dosing and for 16 weeks after stopping treatment with trametinib or 2 weeks after stopping treatment with dabrafenib whichever is longer. Highly effective contraception methods include:

- a. Total abstinence (when this is in line with the preferred and usual lifestyle of the subject). Periodic abstinence (e.g., calendar, ovulation, symptothermal, post-ovulation methods) and withdrawal are not acceptable methods of contraception.
- b. Female sterilization (have had surgical bilateral oophorectomy with or without hysterectomy), total hysterectomy, or tubal ligation at least six weeks before taking study treatment. In case of oophorectomy alone, only when the reproductive status of the woman has been confirmed by follow up hormone level assessment.

- c. Sterilization (at least 6 months prior to screening) for male partners. The vasectomized male partner should be the sole partner for that subject.
- d. Trametinib in combination with dabrafenib only: Placement of a hormonal or non-hormonal intrauterine device (IUD) or intrauterine system (IUS) with a documented failure rate of less than 1% per year.
- e. Trametinib monotherapy only: Use of oral (estrogen and progesterone), injected or implanted combined hormonal methods of contraception or placement of an intrauterine device (IUD) or intrauterine system (IUS), or other forms of hormonal contraception that have comparable efficacy (failure rate <1%), for example hormone vaginal ring or transdermal hormone contraception.

Notes:

- Double-barrier contraception: condom and occlusive cap (diaphragm or cervical/vault caps) with a vaginal spermicidal agent (foam/gel/cream/suppository) are not considered highly effective methods of contraception per Clinical Trial Facilitation Group (CTFG) guidelines ([Clinical Trial Facilitation Group 2014](#)).
- Oral contraceptives are not considered as highly effective methods of contraception for patients taking dabrafenib, due to potential drug-drug interactions with dabrafenib.
- Women are considered post-menopausal and not of child bearing potential if they have had 12 months of natural (spontaneous) amenorrhea with an appropriate clinical profile (i.e. age appropriate, history of vasomotor symptoms) or have had surgical bilateral oophorectomy (with or without hysterectomy), total hysterectomy, or tubal ligation at least six weeks ago. In the case of oophorectomy alone, only when the reproductive status of the woman has been confirmed by follow up hormone level assessment is she considered not of child bearing potential.

10.1.2 Male Subjects

Male patients (including those that have had a vasectomy) must use a condom during intercourse while taking trametinib and/or dabrafenib and not to father a child during the study and for the period of 16 weeks following stopping of study treatment.

10.2 Lactation Restrictions

Female subjects who are lactating must discontinue nursing prior to the first dose of study treatment and must refrain from nursing throughout the treatment period.

11 Data Management

For this study subject data will be entered into the eCRF, transmitted electronically to the sponsor or designee and be combined with data provided from other sources in a validated data system.

Management of clinical data will be performed in accordance with applicable standards and data cleaning procedures to ensure the integrity of the data, e.g., resolving errors and inconsistencies in the data. Adverse events and concomitant medications terms will be coded

using the Medical Dictionary for Regulatory Activities (MedDRA) and a custom drug dictionary.

In all cases, subject initials will not be collected or transmitted to Novartis according to Novartis policy.

12 Data Analysis and Statistical Considerations

12.1 Hypotheses

12.1.1 Part A: Dose-Escalation Phase

No formal statistical hypotheses are being tested. Analysis of the data obtained from this portion of the study will be focused on comparison between dose cohorts and only descriptive methods will be utilized.

12.1.2 Part B: Expansion Cohort

No formal statistical hypotheses are being tested. Analysis of the data obtained from this portion of the study will be focused on evaluating the safety profile, PK/PD relationship, and anti-cancer activity of trametinib for each disease cohort and only descriptive methods will be used in analysis of the data obtained from this study. The range of response rate and the corresponding exact binomial 95% CI is provided in [Section 12.2.2](#), if any objective response is observed in the Expansion Cohort.

12.1.3 Part C: Combination Cohort

No formal statistical hypotheses are being tested. Analysis of the data obtained from this portion of the study will be focused on comparison between dose cohorts and only descriptive methods will be utilized.

12.1.4 Part D: Expansion Cohort with Combination Therapy

No formal statistical hypotheses are being tested. Analysis of the data obtained from this portion of the study will be focused on evaluating the safety profile, PK/PD relationship, and anti-cancer activity of trametinib in combination with dabrafenib for each disease cohort and only descriptive methods will be used in analysis of the data obtained from this study. The range of response rate and the corresponding exact binomial 95% CI is provided in [Section 12.2.4](#), if any objective response is observed in the Expansion Cohort.

12.2 Sample Size Determination

12.2.1 Part A: Dose-Escalation Phase

The total number of subjects to be enrolled in Part A will depend on the number of subjects needed to characterize individual dose cohorts. The sample size is not driven by statistical considerations. However, it is anticipated that approximately 48 subjects will be enrolled.

Given true incidence rates of DLTs, the associated probability of escalating to the next dose level in a 3+3 scheme are provided for reference below in [Table 12-1](#).

Table 12-1 Statistical Basis for Phase I Dose Escalation in a 3+3 Scheme

True incidence of dose-limiting toxicity	10%	20%	30%	40%	50%	60%
Probability of escalating the dose	0.91	0.71	0.49	0.31	0.17	0.08

12.2.2 Part B: Expansion Cohort

The sample size for Part B is based on feasibility, practicality, and what would be sufficient for the characterization of the safety of trametinib and the plasma PK for the populations enrolled. Each of the 4 expansion cohorts will enroll at least 10 evaluable subjects, 5 subjects in each cohort will be under the age of 6 years. Therefore, it is estimated that at least 40 subjects will be enrolled into Part B.

If less than 1 response is observed after 10 subjects complete the study, the treatment could be considered to have insufficient clinical activity in that cohort. The estimated sample size (n=10) for the Part B expansion cohorts was further evaluated using exact binomial distribution probabilities, and the details are provided in [Table 12-2](#). For example, if zero responses are observed among 10 subjects in a cohort [if the response rate (RR)=5%], the chance of declaring the cohort as having insufficient clinical activity after 10 subjects is 60%. If the true RR=15% for trametinib in unresectable low grade gliomas subjects, the chance of declaring the cohort as having insufficient clinical activity after 10 subjects is approximately 20%. [Table 12-4](#) provides the corresponding 95% CIs around potential observed objective response rates given N=10 subjects.

Table 12-2 Exact Binomial Probabilities of Observing 0 and 1 (or more) Responses in 10 Subjects

True RR	Probability of Observing 0 responses in 10 Subjects	Probability of Observing ≥ 1 Responses in 10 Subjects
5%	0.60	0.40
10%	0.35	0.65
15%	0.20	0.80
20%	0.11	0.89
25%	0.056	0.94
30%	0.028	0.97

Table 12-3 Exact Binomial 95% Confidence Intervals Around Potential Observed Objective Responses Rates for 10 Subjects

Observed Objective Response Rate	Exact 95% Confidence Interval (%) (N=10)
10%	0.3, 44.5
20%	2.5, 55.6
30%	6.7, 65.2
40%	12.2, 73.8
50%	18.7, 81.3
60%	26.2, 87.8

Observed Objective Response Rate	Exact 95% Confidence Interval (%) (N=10)
70%	34.8, 93.3

12.2.3 Part C: Combination Cohort

The total number of subjects to be enrolled in Part C will depend on the number of subjects needed to characterize individual dose cohorts. The sample size is not driven by statistical considerations. However, it is anticipated that approximately 18 subjects will be enrolled.

12.2.4 Part D: Expansion Cohort with Combination Therapy

The sample size for Part D is based on feasibility, practicality, and what would be sufficient for the characterization of the safety and preliminary anti-tumor activity of trametinib/ dabrafenib combination and the plasma PK for the populations enrolled. Similar patient populations have been enrolled into the dabrafenib monotherapy phase 1 study, BRF116013 (see [Section 1.3.4.1](#) of this protocol) where it has been shown that it is more practical to enroll patients with LGG than those with LCH. Thus, approximately 20 subjects with LGG and approximately 10 subjects with LCH will be enrolled. Overall approximately 30 subjects will be enrolled into Part D.

The estimated sample size for the LGG and LCH cohorts in Part D is further evaluated using exact binominal distribution probabilities, and the details are provided in [Table 12-4](#) and [Table 12-5](#). For example, if the true RR=20% for trametinib and dabrafenib combination, the probability of observing < 6 responses out of 20 LGG subjects (observed response rate < 30%) is approximately 80%, and the probability of observing < 3 responses out of 10 LCH subjects (observed response rate < 30%) is approximately 68%. If the true RR=50%, the probability of observing at least 6 responses is > 97% given 20 LGG subjects, and the probability of observing at least 3 responses is > 94% given 10 LCH subjects. [Table 12-6](#) provides the corresponding 95% CIs around potential observed objective response rates given N=20 subjects. The corresponding 95% CIs for potential observed response rates given N=10 is shown in [Table 12-3](#).

Table 12-4 Exact Binomial Probabilities of Observing less than 6 and at least 6 Responses in 20 Subjects

True RR	Probability of Observing < 6 responses in 20 Subjects	Probability of Observing ≥ 6 Responses in 20 Subjects
20%	0.80	0.20
25%	0.62	0.38
30%	0.42	0.58
35%	0.25	0.75
40%	0.13	0.87
45%	0.06	0.94
50%	0.02	0.98
55%	0.01	0.99

Table 12-5 Exact Binomial Probabilities of Observing less than 3 and at least 3 Responses in 10 Subjects

True RR	Probability of Observing < 3 responses in 10 Subjects	Probability of Observing ≥ 3 Responses in 10 Subjects
20%	0.68	0.32
25%	0.53	0.47
30%	0.38	0.62
35%	0.26	0.74
40%	0.17	0.83
45%	0.10	0.90
50%	0.05	0.95
55%	0.03	0.97

Table 12-6 Exact Binomial 95% Confidence Intervals around Potential Observed Objective Responses Rates for 20 Subjects

Observed Objective Response Rate	Exact 95% Confidence Interval (%) (N=20)
20%	5.7, 43.7
30%	11.9, 54.3
40%	19.1, 63.9
50%	27.2, 72.8
60%	36.1, 80.9
70%	45.7, 88.1
80%	56.3, 94.3

12.3 Data Analysis Considerations

12.3.1 Analysis Populations

The **All Treated Population** is defined as all subjects who receive at least one dose of study treatment.

This analysis population will be used for summaries of demographic/baseline characteristics and evaluation of anti-cancer activity.

The **Safety Population** consists of all subjects who receive at least one dose of study treatment. Safety will be evaluated based on this analysis population.

The '**DLT Evaluable**' population is defined as those subjects participating in dose determining portion of the study (Part A and 3+3 design portions of Part A extension, Part C and Part C extension) fulfilling the 'All Treated' population criteria and having received an adequate treatment for the first 28 days to enable an appropriate evaluation of study drug related DLTs. Adequate exposure during the first 28 days will be defined as having received >75% of planned study treatment doses, exclusive of missed doses due to treatment-related toxicity. Any subject in the 'All Treated' population who experiences a DLT, as defined in [Section 3.2.3](#), will also be included in the DLT evaluable population regardless of exposure.

The **PK Population** will consist of all subjects from the All Treated Population for whom a PK sample is obtained and analyzed.

The **Response-evaluable Population** is defined as those subjects fulfilling the All Treated Population criteria with a pre-dose and at least one post-dose disease efficacy assessment. In addition, for patients evaluated by RANO criteria, their disease must be ‘measurable’ at baseline to be included in the Response-evaluable Population. This population will be used for sensitivity analysis on the efficacy endpoints.

Additional analysis populations may be defined in the Statistical Analysis Plan (SAP).

12.4 Interim Analysis

12.4.1 Part A: Dose-Escalation

While no formal interim analysis is planned for Part A, safety and PK data will be examined on an ongoing basis to support dose escalation decisions. Prior to determining the dose for the next cohort enrolled, [REDACTED] and the C_{τ} at steady state. For more details of the dose escalation procedure, see [Section 3.2](#).

12.4.2 Part B: Expansion Cohort

An interim analysis is planned after all subjects have been enrolled in B3 cohort and have completed at least 3 post treatment assessments (Weeks 17, 33 and 49) or have discontinued treatment earlier. The results will be used for decision making for future development options and may be used for publications. At this time, no statistical hypothesis testing is planned, and no decision regarding the conduct of this study will be made.

At this interim analysis, the data for Part A subjects will also be analyzed. The data from other disease cohorts for Part B may also be analyzed. In addition, safety and tolerability will be monitored closely on a continued basis.

12.4.3 Part C: Combination Cohort

Prior to opening Part C the available safety and PK data from Parts A and B will be reviewed. Safety and PK data will be examined on an ongoing basis to support dose escalation decisions. Prior to determining the dose for the next cohort enrolled, [REDACTED]

12.4.4 Part D: Expansion Cohort with Combination Therapy

An interim analysis is planned after all subjects have been enrolled in LGG cohort and have completed at least 12 months of treatment or have discontinued treatment earlier. The results will be used for decision making for future development options and may be used for publications. At this time, no statistical hypothesis testing is planned, and no decision regarding the conduct of this study will be made.

At this interim analysis, the data for Part A, B, and C subjects will also be analyzed. The data from other disease cohorts for Part D may also be analyzed. In addition, safety and tolerability will be monitored closely on a continued basis.

Details of the interim analysis will be provided in SAP.

12.4.5 Additional Interim Analyses

Additional interim analyses may be performed to support any health authority or publication requests as and when needed. No efficacy or futility conclusions will be drawn based on these interim analyses.

12.5 Key Elements of Analysis Plan

Data will be listed and summarized according to Novartis reporting standards, where applicable. Complete details will be documented in the SAP. Any deviations from, or additions to, the original analysis plan described in this protocol will be documented in the SAP and final study report.

As it is anticipated that accrual will be spread thinly across centers and summaries of data by center would be unlikely to be information, data from all participating centers will be pooled prior to analysis.

All data up to the time of study completion/withdrawal from study will be included in the analysis, regardless of duration of treatment.

As the duration of treatment for a given subject will depend on efficacy and tolerability, the duration of follow-up will vary between subjects. Consequently there will be no imputation for missing data.

Demographic and baseline characteristics will be summarized.

Subjects who are intra-subject dose escalated will be summarized in the dose level to which they were initially assigned.

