3.7 Intra-subject Dose-Escalation

3.7.1 Part A: Intra-subject Dose Escalation

For subjects enrolled on Part A, an individual subject's dose level may be increased up to the RP2D in the appropriate age cohort if the subject has (all of the following must be true):

- completed at least 56 days of treatment,
- C_{τ} is less than 10 ng/mL,
- not experienced a drug related toxicity greater than Grade 2,
- met criteria for continuation of study treatment ([Section 3.6](#)),
- approval was obtained from a Medical Lead.

Subjects who meet criteria for intrasubject dose escalation will repeat evaluations for the first 28 days (See [Section 3.2.2](#)), including Day 15 PK.

No subject may dose escalate beyond the RP2D or currently evaluated dose for their age group. No subject may have the dose of trametinib escalated above 0.04 mg/kg/day.

For individual subjects who meet criteria for intrasubject dose escalation, data from the escalated dose will not contribute to the definition of MTD or to establishing the recommended dose but will be summarized in the study toxicity data reporting. Data from subjects who are able to increase their dose may be incorporated into PK-PD modelling.

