3.7.3 Part C Intra-subject Dose Escalation

For subjects ages below 6 years enrolled in Part C at 0.025mg/kg/day trametinib dose, an individual subject's trametinib dose level may be increased up to 0.032 mg/kg/day if this dose is found to be tolerated in Part C extension and if the subject has (all of the following must be true):

- completed at least 56 days of treatment,
- not experienced a drug related toxicity greater than Grade 2,
- met criteria for continuation of study treatment ([Section 3.6](#)),

For subjects enrolled in Part C at Dose Level 1, an individual subject's dabrafenib dose may be increased to Dose Level 2 (full dabrafenib RP2D) if the subject has (all of the following must be true):

- completed at least 56 days of treatment,
- not experienced a drug related toxicity greater than Grade 2,
- met criteria for continuation of study treatment ([Section 3.6](#)),

Subjects who meet criteria for intra-subject dose escalation and receive the higher dose may continue to follow the time and event table using the originally assigned study day 1

Subjects may be allowed to re-escalate following dose reduction for AE upon resolution of AE. Please follow guidelines in [Section 3.13](#), [Section 3.14](#) and [Section 3.15](#).

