12.5.1 Anti-Cancer Activity Analyses

The All Treated Population will be used for anti-cancer activity analyses. Since this is a Phase I study, anti-cancer activity will be evaluated by investigator assessment based on clinical evidence and response criteria provided in Appendix 3 through Appendix 7. If data warrant, the response data will be summarized by disease cohort and by dose level. Anti-cancer activity analyses will also be performed based on Response-Evaluable population as sensitivity analysis.

In a supportive analysis, for LGG and NF-1 patients, anti-cancer activity will also be evaluated by independent review assessment based on clinical evidence and response criteria provided in Appendix 5 and 6 respectively.

Correlation analysis will be conducted to explore any relationship between the subject's PK or PD evaluations and tumor response based on disease specific response criteria provided in [Appendix 3](#) through [Appendix 7](#).

Full details will be specified in the SAP.

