12.5.2 Safety Analyses

The Safety Population will be used for the analysis of safety data. All serially collected safety endpoints (e.g., laboratory tests, vital signs, ECGs) will be summarized according to the scheduled, nominal visit at which they were collected and across all on-treatment time points

using a “worst-case” analysis. Complete details of the safety analyses will be provided in the SAP.

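### Section 12.5 reports escalated subjects only under their starting dose, so descriptive by-dose safety and response tables can credit that dose with events first seen at a higher one

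*Protocol*

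**What the plan says.** Section 12.5 sets two rules that act together. On escalated subjects: "Subjects who are intra-subject dose escalated will be summarized in the dose level to which they were initially assigned". On the data used: "All data up to the time of study completion/withdrawal from study will be included in the analysis, regardless of duration of treatment".

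The sections that produce the tables follow on from these:
- Section 12.5.2 has serial safety data "summarized according to the scheduled, nominal visit at which they were collected and across all on-treatment time points", using a worst-case analysis.
- Section 12.5.1 says: "If data warrant, the response data will be summarized by disease cohort and by dose level".
- Sections 12.1.1 (Part A) and 12.1.3 (Part C) say the analysis "will be focused on comparison between dose cohorts and only descriptive methods will be utilized".

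Escalation routes, each needing at least 56 days of treatment and no drug-related toxicity above Grade 2:
- Part A (Section 3.7.1): up to the RP2D for the age cohort. A trough below 10 ng/mL and Medical Lead approval are also required.
- Part B (Section 3.7.2): under 6 years, trametinib 0.025 to 0.032 mg/kg/day, if tolerated in the Part A extension.
- Part C (Section 3.7.3): the same trametinib step under 6 years, if tolerated in the Part C extension. For Dose Level 1 subjects the "dabrafenib dose may be increased to Dose Level 2 (full dabrafenib RP2D) if the subject has" met the listed conditions.

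Section 3.7.1 adds that, for escalated Part A subjects, "data from the escalated dose will not contribute to the definition of MTD or to establishing the recommended dose". It goes on to say that these data will appear in the toxicity reporting, without naming the dose level.

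**The concern.** Parts A and C are meant to describe how dose cohorts differ. Under Section 12.5 a starting-dose row holds everything that happens to its subjects, including what happens after the dose is raised. If events or responses are more frequent at the higher dose, the lower dose looks more toxic and more active than it was, and the difference between doses shrinks.

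Part B has a single starting dose, so there is no between-dose contrast to distort. There the question is what the 0.025 mg/kg/day results represent when some of the under-6 subjects were taking 0.032.

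The tables matter outside the trial: Sections 12.4.2 and 12.4.4 say interim results will be used for development decisions and may be published.

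**Working it through.** **1. Can escalated-dose data reach the dose-finding decisions?**
- DLTs count only in the first 28 days (Sections 3.2.2 and 3.2.3). The PK target uses the Day 15 trough (Sections 3.2.2 and 3.2.5).
- Escalation needs at least 56 days in Parts A, B and C.
- Gap: 56 − 28 = 28 days at least. No escalated-dose event can be a starting-dose DLT.
- Table 12-1 is the plan's own figure for the 3+3 scheme. The probability of escalating is (1−p)³ + 3p(1−p)²(1−p)³. At p = 0.30 this is 0.343 + 0.151 = 0.494, against 0.49 printed. For p = 10% to 60% the formula gives 0.906, 0.709, 0.494, 0.309, 0.172 and 0.082; all six entries reproduce. The Section 12.5 rule does not enter this calculation.

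**2. How large are the dose changes being merged?**
- Part A, 0.0125 to 0.025 mg/kg/day: factor 2.
- Part C, dabrafenib 50% to 100% of RP2D: factor 2.
- Under 6 years, 0.025 to 0.032 mg/kg/day: 0.032/0.025 = 1.28.

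**3. How does escalation sit against response assessment?**
Counting weeks as in Table 7-1 (Week 3 is Day 15), Week 9 is Day 57, Week 13 is Day 85 and Week 17 is Day 113. The earliest escalation, after 56 completed days, coincides with the first Week 9 assessment. LCH subjects are first assessed at Week 13 (Table 7-4) and cohort B3 at Week 17 (Table 7-5). A B3 subject escalated on Day 57 would have 113 − 57 = 56 days at the higher dose before the first response MRI, yet any response is reported at 0.025.

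**4. How far could a descriptive rate move?**
The documents give no event rates and no number escalated, so these are assumptions:
- pL: rate of events first seen on the starting dose
- pH: rate in subjects who started at the higher dose
- f: share of subjects still free of the event who are escalated
- q: their chance of a first event after escalation

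Reported starting-dose rate = pL + f(1−pL)q. With pL = 10% and pH = 30% (difference 20 points):

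| f | q | Reported starting-dose rate | Reported difference |
|---|---|---|---|
| 0 | any | 10% | 20 points |
| 25% | 10% | 0.10 + 0.25×0.90×0.10 = 12.25% | 17.75 points |
| 25% | 20% | 14.5% | 15.5 points |
| 50% | 20% | 0.10 + 0.50×0.90×0.20 = 19% | 11 points |
| 100% | 20% | 28% | 2 points |
| 100% | 30% | 37% | −7 points |

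With pL = 20% and pH = 40%, f = 50% and q = 20% give 0.20 + 0.50×0.80×0.20 = 28%, a reported difference of 12 points. The formula shows how many events change rows. It does not give a net bias, because some of those events might also have occurred had the subject stayed on the lower dose.

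**5. Ceilings.** A subject escalated on the first possible day and treated for a year spends (365 − 56)/365 = 85% of the time at the higher dose. One subject is 17% to 33% of a cohort of six to three. The Part B under-6 minimum, 4 per cohort (Section 5.1) or 5 (Section 12.2.2), is 16 to 20 subjects over four cohorts. These are upper limits on exposure or eligibility, not counts of misattributed events.

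**The case against.** A reader might infer that the rule weakens the evidence for the RP2D. The documents do not support that. The 28-day DLT window and Day 15 trough close before escalation can begin, and Section 3.7.1 keeps escalated-dose data out of the Part A MTD and recommended dose. Sections 3.7.1 and 12.5 are also compatible: one governs the dose decision, the other the reporting. The amendment rationales add that RP2Ds have been declared and all cohorts are closed.

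The other arguments have some force:
- *Summarising by initial dose is a recognised as-assigned view, and the comparison is descriptive.* True, and a reason to keep the table. But it is the only by-dose summary the protocol names for these subjects, and its rows mix doses without saying so.
- *Details are left to the SAP.* The SAP was not available for this review and may already hold extra tables. The attribution rule itself, however, is stated in the protocol.
- *Cutting the data at escalation has its own bias.* This stands. Escalated subjects are selected for tolerance, pre-escalation follow-up could be as short as 56 days, and a B3 subject escalated before Week 17 could never count as an initial-dose responder. Truncation should not become the main analysis.
- *Exposure share is not event share.* Also right: Section 1.7.2 notes that about half of first pyrexia occurrences in adults on the combination came in the first month.

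**Conclusion.** The point holds as a defect of descriptive reporting. In Parts A and C, by-dose safety and response summaries can place events first seen at a higher dose under the starting dose; in Part B the same applies to the 0.025 mg/kg/day results of escalated under-6 subjects. The DLT, MTD and RP2D decisions are untouched.

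The size cannot be determined from the protocol. It is zero if nobody escalated. Under the assumed 10% and 30% rates, with f from 25% to 100% and q from 10% to 30%, the reported difference runs from 17.75 to −7 points instead of 20.

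Two places are left unclear by the same rule. Escalated Part A subjects repeat the first 28 days of evaluations, including Day 15 PK (Section 3.7.1), and Section 12.5 read literally would file that trough under the lower dose. Section 3.10.1 brings Part A responses at the RP2D into the Part B analysis without saying whether subjects who escalated to the RP2D are included.

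**What to change.** Keep the initial-dose summary and add to Section 12.5:
1. Adverse events, worst-case safety values, post-escalation PK and first documented responses are also summarised by the dose being taken at onset, assessment or sampling.
2. Post-escalation data go in a separate column and are not pooled with subjects who started at the higher dose.
3. The number and timing of escalations are reported by part and starting dose.
4. A cross-reference to Section 3.7.1 confirms that these data do not enter the Part A MTD or recommended dose.
5. Section 3.10.1 states whether Part A subjects escalated to the RP2D count in the Part B response analysis.

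The cost is some wording and a few tables. Treatment dates and dose escalations are already recorded (Section 4.4, Table 7-4). Pre-escalation follow-up will be short and the post-escalation group is selected for tolerance, so the added tables should be labelled supplementary and descriptive. If the SAP already contains them, a cross-reference from Section 12.5 and the clarification of Section 3.10.1 are enough.
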